9.2.3 Study visits

9.2.3.1 Visit 1: Baseline

At Visit 1, the informed consent is obtained from the patient using the data release consent form. After obtaining written consent, the following data will be collected.

- Visit date
- Signed date of data release consent
- Information on diagnosis of GPP and flare: date of diagnosis of GPP and this flare, average number of flares per year and family history of psoriasis
- Information on inclusion / exclusion criteria
- Demographics: gender, age (year and month of birth), current pregnancy and breastfeeding status (female only), smoking status, alcohol intake status
- Medical history: within 6 months
- Past / concomitant medications or non-drug therapy: within 6 months
- Physical examination: blood pressure, pulse rate, weight, height, body temperature
- GPPGA pustulation sub-score
- GPPGA score
- GPPASI (if available)
- Pain VAS (if available)
- PSS (if available)
- IL-36RN mutation status (if available)
- C-reactive protein (CRP) level (if available)
- Other laboratory test results (if available)
- Spesolimab IV administration status: date of administration, total daily dose

At Visit 1, the patient will be requested to contact the investigator in the event of any AEs noted after initiating Spesolimab IV treatment.

9.2.3.2 Visit 2: 1 week from Visit 1

After 1 week from Visit 1, the patient returns for follow-up. The following data will be collected.

- Visit date
- Physical examination: blood pressure, pulse rate, body temperature
- Concomitant medications or non-drug therapy
- Any changes in the Spesolimab IV administration status
- Subsequent exposure to subcutaneous Spesolimab
- GPPGA pustulation sub-score
- GPPGA score
- GPPASI (if available)
- CRP level (if available)
- Other laboratory test results (if available)
- Safety assessment: any AEs noted
- Study completion status (if applicable)
- Investigator's overall effectiveness assessment (if applicable)

9.2.3.3 Visit 3: 4 weeks from Visit 1

After 4 weeks from Visit 1, the patient returns for follow-up. The following data will be collected.

- Visit date
- Physical examination: blood pressure, pulse rate, body temperature
- Concomitant medications or non-drug therapy
- Any changes in the Spesolimab IV administration status
- Subsequent exposure to subcutaneous Spesolimab
- GPPGA pustulation sub-score
- GPPGA score
- GPPASI (if available)
- Pain VAS (if available)
- PSS (if available)
- CRP level (if available)

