9.3.2 Outcomes

9.3.2.1 Primary outcomes

The primary outcomes are the safety outcomes until study completion, calculated as the incidence of:

- Adverse events (AEs)
- Adverse drug reactions (ADRs)
- Serious adverse events (SAEs)
- Serious adverse drug reactions (SADRs)
- Unexpected adverse drug reactions
- Adverse events of special interest (AESIs)
- Adverse events leading to temporary or permanent discontinuation
- Adverse events leading to death

Assessment of safety:

- AE (event name / symptom / sign)
- Onset date and end date
- Intensity (mild / moderate / severe)
- Seriousness (serious / non-serious)
- Outcome of the event (recovered / not yet recovered / sequela / fatal / unknown)
- Causality (certain / probable-likely / possible / unlikely / conditional-unclassified / unassessable-unclassifiable)
- Action taken with study drug due to AE (dose not changed / dose reduced / dose increased / drug withdrawn / not applicable)
- AESIs (systemic hypersensitivity reactions including infusion reactions and anaphylactic reaction / severe infections / opportunistic and mycobacterium tuberculosis infections)

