9.7.1.2 Number of cases to safety assessment

These include those who signed the data release consent form to participate in this study, took Spesolimab IV once at least, and were followed up by the investigator once or more.

Based on the MFDS guideline, the cases below shall be excluded from safety analysis (defined below):

- a. Patients who did not signed (signature missing), or patients who signed on the data release consent form prior to the contract date
- b. Patients who took Spesolimab IV prior to the contract date
- c. Patients who took Spesolimab IV prior to signing the data release consent form
- d. Patients who have not taken Spesolimab IV
- e. Patients who do not meet the inclusion/exclusion criteria
- f. Follow-up failure: Patients whose safety information cannot be obtained due to lost-to-follow-up
- g. Patients who were prescribed Spesolimab IV for indications outside the local label

However, cases enrolled during the complete enumeration period within 2 years of product launch will be included in the safety set even if the patients who took Spesolimab IV prior to the contract date or prior to signing the data release consent form.

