The term Adverse Event of Special Interest (AESI) relates to any specific AE that has been identified at the project level as being of particular concern for prospective safety monitoring and safety assessment within this study, e.g. the potential for AEs based on knowledge from other compounds in the same class.

The following are considered as AESIs:

- Systemic hypersensitivity reactions including infusion reactions and anaphylactic reactions
- Severe infection
- Opportunistic and mycobacterium tuberculosis infections

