11.2 ADVERSE EVENT AND SERIOUS ADVERSE EVENT COLLECTION AND REPORTING

The investigator shall maintain and keep detailed records of all AEs in their patient files.

Collection of adverse events

The study is a non-interventional study in real-world situation and will be conducted within the conditions of the approved marketing authorization. For this reason, the following AE collection and reporting requirements have been defined.

All serious adverse events, non-serious adverse events and AESIs occurring from the signing date on data release consent form to the end of the study need to be collected, documented and reported to the sponsor using the AE page of eCRF.

The investigator carefully assesses whether an AE constitutes an ADR using the information below.

Causal relationship of adverse event

The definition of an adverse reaction implies at least a reasonable possibility of a causal relationship between a suspected medicinal product and an AE. An adverse reaction, in contrast to an AE, is characterized by the fact that a causal relationship between a medicinal product and an occurrence is suspected.

Medical judgment should be used to determine the relationship, considering all relevant factors, including pattern of reaction, temporal relationship, de-challenge or re-challenge, confounding factors such as concomitant medication, concomitant diseases and relevant history.

Arguments that may suggest a **reasonable causal relationship** could be:

- The event is consistent **with the known pharmacology** of the drug
- The event is known to be caused by or **attributed to the drug class**
- A **plausible time to onset of the event** relative to the time of drug exposure
- Evidence that the **event is reproducible** when the drug is re-introduced
- **No medically sound alternative etiologies** that could explain the event (e.g. preexisting or concomitant diseases, or co-medications).
- The event is typically **drug-related and infrequent in the general population** not exposed to drugs (e.g. Stevens-Johnson syndrome).
- An indication of dose-response (i.e. greater effect size if the dose is increased, smaller effect size if dose is diminished).

Arguments that may suggest that there is **no reasonable possibility of a causal relationship** could be:

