- Unlikely: An event with a temporal relationship to drug administration which makes a causal relationship improbable, and in which other drugs, chemicals or underlying disease provide plausible explanations.

Intensity of adverse event

The intensity of the AE should be judged based on the following:

- Mild: Awareness of sign(s) or symptom(s) which is / are easily tolerated
Moderate: Enough discomfort to cause interference with usual activity
Severe: Incapacitating or causing inability to work or to perform usual activities

Pregnancy:

In rare cases, pregnancy might occur in a ONIS. Once a patient has been enrolled in the study and has taken study medication, the investigator must report any drug exposure during pregnancy in a study participant within 7 days by means of Part A of the Pregnancy Monitoring Form to the sponsor's unique entry point.

The outcome of the pregnancy associated with the drug exposure during pregnancy must be followed up and reported to the sponsor's unique entry point on the Pregnancy Monitoring Form (Part B).

The investigator site file (ISF) will contain the Pregnancy Monitoring Form (Part A and B). As pregnancy itself is not to be reported as an AE, in the absence of an accompanying AE, only the Pregnancy Monitoring Form and not the ONIS AE form is to be completed. If there is an AE associated with the pregnancy a ONIS AE form must be completed in addition.

Expedited Reporting of AEs and Drug Exposure during Pregnancy to Boehringer Ingelheim Patient Safety and Pharmacovigilance

The following must be reported by the investigator on the ONIS AE form ([Annex 8](#)) and / or Pregnancy Monitoring Form ([Annex 9](#)) from signing the informed consent onwards until the end of the study and provide Boehringer Ingelheim unique entry point:

Boehringer Ingelheim contact details

Local Patient Safety Lead (LPSL)

Tel: [REDACTED]

Fax: [REDACTED]

Address: [REDACTED]

Type of Report	Timeline
All SAEs	immediately within 24 hours
All protocol specified AESIs	Immediately within 24 hours
All non-serious AEs	7 calendar days
Drug exposure during pregnancy	7 calendar days

The same timelines apply if follow-up information becomes available for the respective events. In specific occasions the Investigator could inform the Sponsor upfront via telephone. This does not replace the requirement to complete the AE page of the eCRF and the ONIS AE form and report the ONIS AE form.

Information required

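### Complete-enumeration patients who consent on a later day than their first infusion count in the safety set, but adverse events need be collected only from the consent date

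*Protocol*

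**What the plan says.** **Who is counted.** Section 9.7.1.2 lists the exclusions from the safety analysis. Item b removes patients dosed before the contract date, and item c removes this group: "Patients who took Spesolimab IV prior to signing the data release consent form". The closing paragraph then lifts both items for cases enrolled in the complete-enumeration period, which "will be included in the safety set even if the patients who took Spesolimab IV prior to the contract date or prior to signing" the consent form. Section 9.7.2 bases the safety analyses on everyone who received at least one dose.

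**What is collected.** Section 11.2 requires serious events, non-serious events and events of special interest to be documented in the eCRF when "occurring from the signing date on data release consent form to the end of the study". The expedited-reporting part of the same section has the same start: "from signing the informed consent onwards until the end of the study". Neither makes an exception for the patients whom 9.7.1.2 readmits.

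**What is estimated.** Section 9.3.2.1 states: "The primary outcomes are the safety outcomes until study completion, calculated as the incidence of" a list of event classes that includes events of special interest. It gives an end point but no start point. The first event of special interest in section 11.1 is "Systemic hypersensitivity reactions including infusion reactions and anaphylactic reactions".

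**The visit clock.** For Visit 1, section 9.2.3.1 says: "After obtaining written consent, the following data will be collected". Later visits are timed from Visit 1; for Visit 2 the text is: "After 1 week from Visit 1, the patient returns for follow-up".

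**The concern.** An incidence needs a numerator and a denominator that cover the same period at risk. For the readmitted patients they do not: exposure begins at the infusion, while mandatory event collection begins at consent. Section 9.3.1 gives the recommended treatment as a single dose, so the first infusion is the main exposure, and the days right after it are when infusion and hypersensitivity reactions would be expected. A patient whose window opens later is counted as at risk of such a reaction, but a reaction that occurred need not be entered.

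Item c, left alone, would have prevented this mismatch. The exception removes that protection, and nothing in 11.2 replaces it. The amendment table in section 5 lists changes to 9.1, 9.2.2.2, 9.5 and 9.7.1.2, but none to 11.2.

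This concerns the primary outcome in a study of 21 patients, where one or two unrecorded reactions would visibly change the result. It also cannot be left to a statistical analysis plan, because no analysis recovers events that sites were never told to record.

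**Working it through.** **1. Nothing to reproduce.** Section 9.5 sets the target of 21 from prevalence and market conditions. There is no precision calculation. The check therefore compares two rules and adds an illustration of scale.

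**2. Which patients are affected.** Three conditions must all hold:

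- The patient was enrolled in the complete-enumeration period (within two years of launch). Later patients dosed before consent remain excluded under item c, so for them there is no mismatch.
- Consent was signed on a later calendar day than the first infusion. The window in 11.2 opens on the signing date, so same-day consent still captures infusion-day events.
- The event began before the signing date.

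The second condition is met automatically for patients readmitted from item b. Item a excludes anyone who consented before the contract date, and the exception does not lift item a. A patient dosed before the contract date must therefore have signed on or after that date, hence on a later day than the infusion.

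**3. Is the group likely to exist?** The exception was written for it. Section 9.5 commits to data from all patients treated within two years of launch. Section 6 starts data collection in March 2025, while interim reports, timed from market approval, begin in April 2024. The launch date and the number of such patients are not given.

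**4. Illustration.** Assumptions, none from the protocol: *k* of the 21 patients have no early events captured, the true early-reaction risk is *p* = 10%, and intervals are exact (Clopper-Pearson; the protocol names no method).

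- Expected recorded risk = *p* × (21 − *k*)/21
- Chance of recording at least one event = 1 − (1 − *p*)^(21 − *k*)
- Upper 95% limit with zero events in *n* patients = 1 − 0.025^(1/*n*)

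| *k* | (21 − *k*)/21 | Recorded risk if true risk is 10% | Chance of at least one recorded | Upper limit reported (0/21) | Upper limit from those observed |
|---|---|---|---|---|---|
| 0 | 1.00 | 10.0% | 89.1% | 16.1% | 16.1% (0/21) |
| 3 | 0.86 | 8.6% | 85.0% | 16.1% | 18.5% (0/18) |
| 7 | 0.67 | 6.7% | 77.1% | 16.1% | 23.2% (0/14) |
| 10 | 0.52 | 5.2% | 68.6% | 16.1% | 28.5% (0/11) |

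The scaling factor does not depend on *p*. A true risk of 15% would be recorded as 12.9%, 10.0% or 7.9% for *k* = 3, 7 or 10.

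**5. The visit clock, for the same patients.** Section 9.7.1.3 removes from the effectiveness set those excluded from the safety set, so readmitted patients can enter it. If Visit 1 falls after the infusion, Weeks 1, 4 and 24 are counted from too late a day, and a score taken at Visit 1 is a treated value. The four secondary outcomes in 9.3.2.2 are states at Week 1 or Week 4 (pustulation sub-score 0, GPPGA 0 or 1). A treated baseline does not alter them, although their timing can shift. Changes from baseline are affected directly, but 9.7.3 treats their comparison as exploratory.

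**The case against.** The strongest reply is that 11.2 sets a minimum and does not bar earlier events. Several passages carry no consent cut-off. The abstract takes as its safety outcome all events reported in dosed patients and names medical records as the data source. Visit 1 asks patients to report events noted after treatment starts. Section 9.7.5 uses all available data, and 11.2 has investigators keep records of all events in the patient file. Early events may therefore surface. This stands as a limit on the claim: it is wrong to say that these events will be lost. But none of these passages requires an event before consent to be entered in the eCRF, and the passages that do set a start date set it at consent.

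A reader might also infer more than the documents support:

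- *That every patient dosed before consent is affected.* Item c still excludes those outside the enumeration period. Sections 9.1 and 9.4 also start enrolment with patients first dosed after the study start date, which would narrow the group, although 9.5 is worded more widely.
- *That infusion-day events are always missed.* Same-day consent captures them, and a patient given a further infusion after consent is observed for that one.
- *That patients had to survive to be included.* Section 10.1 allows a legally accepted representative to consent, although inclusion criterion 4 speaks of patients who signed.
- *That the effectiveness results rest on treated baselines.* The flow chart records administration at Week 0, so Visit 1 is written as the dosing visit. Nothing forbids entering a charted pre-dose score, and 9.7.1.3 requires visits to follow the schedule.

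Finally, the analyses are exploratory and no hypothesis is tested. That lowers the stakes for any p-value, but not for an incidence reported to the regulator as the primary result.

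**Conclusion.** The conflict between 9.7.1.2 and 11.2 is in the current text and bears on the primary outcome. For enumeration-period patients who consent on a later day than their first infusion, the protocol counts the patient but does not require the events between infusion and consent. Early-event incidence, notably for infusion and hypersensitivity reactions, can therefore be biased down, and a zero count would carry too low an upper limit.

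The size is unknown. The example of 7 unobserved patients (16.1% reported against 23.2% supported) rests on an assumed count and on no early capture in any of the 7. It concerns early reactions only and does not measure bias in adverse-event incidence over the full 24 weeks. If every such patient consented on the infusion day, or if sites entered earlier events of their own accord, the bias would be small or absent. The visit-clock issue is a secondary clarification for the same patients.

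**What to change.** **Section 11.2, collection and expedited reporting.** Start both at the earlier of consent and first Spesolimab IV infusion. For patients dosed before consent, require events to be abstracted from the medical record back to the first infusion, under the signed data release consent.

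**Where that record cannot be obtained.** Leave the patient out of the denominator for early events, or report these patients separately.

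**Section 9.2.3, for the same patients.** State that baseline is the last charted assessment before first infusion and that Weeks 1, 4 and 24 are counted from first infusion. This cannot recreate a Week 1 assessment that was never made, but it prevents a mislabelled one.

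**Cost.** Wording in two sections, one eCRF instruction, and chart abstraction for what may be only a few patients. The downside is that mild events before consent may be recorded less completely than those seen prospectively, which the report should say.

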11.3 REPORTING TO HEALTH AUTHORITIES

AE reporting to regulatory agencies will be done by MAH according to local and international regulatory requirements.

12. PLANS FOR DISSEMINATING AND COMMUNICATING STUDY RESULTS

According to the local regulations, periodic reports and the study final report will be submitted to MFDS.

The rights of the investigator and of the sponsor with regard to publication of the results of this study are described in the investigator contract. As a general rule, no study results should be published prior to finalization of the Study Report.

ANNEX 1. LIST OF STAND-ALONE DOCUMENTS

None

ANNEX 2. ENCePP CHECKLIST FOR STUDY PROTOCOLS

Doc.Ref. EMA/540136/2009

ENCePP Checklist for Study Protocols (Revision 4)

Adopted by the ENCePP Steering Group on 15/10/2018

The European Network of Centres for Pharmacoepidemiology and Pharmacovigilance (ENCePP) welcomes innovative designs and new methods of research. This Checklist has been developed by ENCePP to stimulate consideration of important principles when designing and writing a pharmacoepidemiological or pharmacovigilance study protocol. The Checklist is intended to promote the quality of such studies, not their uniformity. The user is also referred to the ENCePP Guide on Methodological Standards in Pharmacoepidemiology, which reviews and gives direct electronic access to guidance for research in pharmacoepidemiology and pharmacovigilance.

For each question of the Checklist, the investigator should indicate whether or not it has been **addressed in the study protocol. If the answer is "Yes",** the section number of the protocol where this issue has been discussed should be specified. It is possible that some questions do not apply to a particular study (for example, in the case of an innovative study design). In this case, the answer 'N/A' (Not Applicable) can be checked and the "Comments" field included for each section should be used to explain why. The "Comments" field can also be used to elaborate on a "No" answer.

This Checklist should be included as an Annex by marketing authorisation holders when submitting the protocol of a non-interventional post-authorisation safety study (PASS) to a regulatory authority (see the Guidance on the format and content of the protocol of non-interventional post-authorisation safety studies). The Checklist is a supporting document and does not replace the format of the protocol for PASS presented in the Guidance and Module VIII of the Good pharmacovigilance practices (GVP).

Study title:
A regulatory requirement non-interventional study to monitor the safety and effectiveness of Spesolimab in Korean patients with flares with generalized pustular psoriasis

EU PAS Register® number: EUPAS1000000278
Study reference number (if applicable): N/A

Section 1: Milestones	Yes	No	N/A	Section Number
1.1 Does the protocol specify timelines for				
1.1.1 Start of data collection ¹				6
1.1.2 End of data collection ²				6
1.1.3 Progress report(s)				
1.1.4 Interim report(s)				6

¹Date from which information on the first study is first recorded in the study dataset or, in the case of secondary use of data, the date from which data extraction starts.

²Date from which the analytical dataset is completely available.

1.1.5 Registration in the EU PAS Register®				6
1.1.6 Final report of study results.				6

Comments:

1.1.3: According to the local regulation, periodic reports will be submitted to the regulatory authority.

Section 2: Research question	Yes	No	N/A	Section Number
2.1 Does the formulation of the research question and objectives clearly explain:				8
2.1.1 Why the study is conducted? (e.g. to address an important public health concern, a risk identified in the risk management plan, an emerging safety issue)				7
2.1.2 The objective(s) of the study?				8
2.1.3 The target population? (i.e. population or subgroup to whom the study results are intended to be generalised)				9.2.2
2.1.4 Which hypothesis(-es) is (are) to be tested?				
2.1.5 If applicable, that there is no a priori hypothesis?				

Comments:

2.1.4: This study is a regulatory PMS. This study is conducted using a use result surveillance method according to local guidelines.

Section 3: Study design	Yes	No	N/A	Section Number
3.1 Is the study design described? (e.g. cohort, case-control, cross-sectional, other design)				9.1
3.2 Does the protocol specify whether the study is based on primary, secondary or combined data collection?				9
3.3 Does the protocol specify measures of occurrence? (e.g., rate, risk, prevalence)				
3.4 Does the protocol specify measure(s) of association? (e.g. risk, odds ratio, excess risk, rate ratio, hazard ratio, risk/rate difference, number needed to harm (NNH))				
3.5 Does the protocol describe the approach for the collection and reporting of adverse events/adverse reactions? (e.g. adverse events that will not be collected in case of primary data collection)				11

Comments:

3.3, 3.4: This study is a regulatory PMS. This study is conducted using a use result surveillance method according to local guidelines.

Section 4: Source and study populations	Yes	No	N/A	Section Number
4.1 Is the source population described?				9.2.2
4.2 Is the planned study population defined in terms of:				
4.2.1 Study time period				9.2.3.6
4.2.2 Age and sex				9.2.2
4.2.3 Country of origin				9.2.2
4.2.4 Disease/indication				9.2.2
4.2.5 Duration of follow-up				9.2.3.6
4.3 Does the protocol define how the study population will be sampled from the source population? (e.g. event or inclusion/exclusion criteria)				9.2.2

Comments:

--

Section 5: Exposure definition and measurement	Yes	No	N/A	Section Number
5.1 Does the protocol describe how the study exposure is defined and measured? (e.g. operational details for defining and categorising exposure, measurement of dose and duration of drug exposure)				9.2.3
5.2 Does the protocol address the validity of the exposure measurement? (e.g. precision, accuracy, use of validation sub-study)				
5.3 Is exposure categorised according to time windows?				
5.4 Is intensity of exposure addressed? (e.g. dose, duration)				9.3.1
5.5 Is exposure categorised based on biological mechanism of action and taking into account the pharmacokinetics and pharmacodynamics of the drug?				
5.6 Is (are) (an) appropriate comparator(s) identified?				

Comments:

5.2, 5.3, 5.5, 5.6: This study is a regulatory PMS. This study is conducted using a use result surveillance method according to local guidelines.

Section 6: Outcome definition and measurement	Yes	No	N/A	Section Number
6.1 Does the protocol specify the primary and secondary (if applicable) outcome(s) to be investigated?				9.3.2

Section 6: Outcome definition and measurement	Yes	No	N/A	Section Number
6.2 Does the protocol describe how the outcomes are defined and measured?				
6.3 Does the protocol address the validity of outcome measurement? (e.g. precision, accuracy, sensitivity, specificity, positive predictive value, use of validation sub-study)				
6.4 Does the protocol describe specific outcomes relevant for Health Technology Assessment? (e.g. HROoL, QALYS, DALYS, health care services utilisation, burden of disease or treatment, compliance, disease management)				

Comments:

6.3, 6.4: This study is a regulatory PMS. This study is conducted using a use result surveillance method according to local guidelines.

Section 7: Bias	Yes	No	N/A	Section Number
7.1 Does the protocol address ways to measure confounding? (e.g. confounding by indication)				9.9.2
7.2 Does the protocol address selection bias? (e.g. healthy user/adherer bias)				9.1, 9.2
7.3 Does the protocol address information bias? (e.g. misclassification of exposure and outcomes, time-related bias)				

Comments:

7.3: This study is a regulatory PMS. This study is conducted using a use result surveillance method according to local guidelines.

Section 8: Effect measure modification	Yes	No	N/A	Section Number
8.1 Does the protocol address effect modifiers? (e.g. collection of data on known effect modifiers, sub-group analyses, anticipated direction of effect)				

Comments:

This study is a regulatory PMS. This study is conducted using a use result surveillance method according to local guidelines.

Section 9: Data sources	Yes	No	N/A	Section Number
9.1 Does the protocol describe the data source(s) used in the study for the ascertainment of:				
9.1.1 Exposure? (e.g. pharmacy dispensing, general practice prescribing, claims data, self-report, face-to-face interview)				

Section 9: Data sources	Yes	No	N/A	Section Number
9.1.2 Outcomes? (e.g. clinical records, laboratory markers or values, claims data, self-report, patient interview including scales and questionnaires, vital statistics)				9.4
9.1.3 Covariates and other characteristics?				9.4
9.2 Does the protocol describe the information available from the data source(s) on:				
9.2.1 Exposure? (e.g. date of dispensing, drug quantity, dose, number of days of supply prescription, daily dosage, prescriber)				9.2.3
9.2.2 Outcomes? (e.g. date of occurrence, multiple event, severity measures related to event)				9.2.3
9.2.3 Covariates and other characteristics? (e.g. age, sex, clinical and drug use history, co-morbidity, co-medications, lifestyle)				9.2.3
9.3 Is a coding system described for:				
9.3.1 Exposure? (e.g. WHO Drug Dictionary, Anatomical Therapeutic Chemical (ATC) Classification System)				9.7.1
9.3.2 Outcomes? (e.g. International Classification of Diseases (ICD), Medical Dictionary for Regulatory Activities (MedDRA))				9.7.1
9.3.3 Covariates and other characteristics?				9.7.1
9.4 Is a linkage method between data sources described? (e.g. based on a unique identifier or other)				

Comments:

9.1.1, 9.4: This study is a regulatory PMS. This study is conducted using a use result surveillance method according to local guidelines.

Section 10: Analysis plan	Yes	No	N/A	Section Number
10.1 Are the statistical methods and the reason for their choice described?				9.7
10.2 Is study size and/or statistical precision estimated?				
10.3 Are descriptive analyses included?				
10.4 Are stratified analyses included?				
10.5 Does the plan describe methods for analytic control of confounding?				
10.6 Does the plan describe methods for analytic control of outcome misclassification?				
10.7 Does the plan describe methods for handling missing data?				9.7.4
10.8 Are relevant sensitivity analyses described?				

Comments:

10.2, 10.4, 10.5, 10.6, 10.8: This study is a regulatory PMS. This study is conducted using a use result surveillance method according to local guidelines.

Section 11: Data management and quality control	Yes	No	N/A	Section Number
11.1 Does the protocol provide information on data storage? (e.g. software and IT environment, database maintenance and anti-fraud protection, archiving)				9.6, 9.8
11.2 Are methods of quality assurance described?				9.10.1
11.3 Is there a system in place for independent review of study results?				

Comments:

11.3: This study is a regulatory PMS. This study is conducted using a use result surveillance method according to local guidelines.

Section 12: Limitations	Yes	No	N/A	Section Number
12.1 Does the protocol discuss the impact on the study results of:				
12.1.1 Selection bias?				9.1, 9.2
12.1.2 Information bias?				9.9
12.1.3 Residual/unmeasured confounding? (e.g. anticipated direction and magnitude of such biases, validation sub-study, use of validation and external data, analytical methods).				9.9
12.2 Does the protocol discuss study feasibility? (e.g. study size, anticipated exposure uptake, duration of follow-up in a cohort study, patient recruitment, precision of the estimates)				

Comments:

12.2: This study is a regulatory PMS. This study is conducted using a use result surveillance method according to local guidelines.

Section 13: Ethical/data protection issues	Yes	No	N/A	Section Number
13.1 Have requirements of Ethics Committee/ Institutional Review Board been described?				10
13.2 Has any outcome of an ethical review procedure been addressed?				10
13.3 Have data protection requirements been described?				10

Comments:

